## 7 STUDY SCHEDULE & PROCEDURES

Study eligible patients who are considered as candidates for sarecycline treatment as part of usual care Acne management will be screened, consented and recruited into the study, followed for up to 12 weeks post-index date, encompassing four distinct data collection encounters. With 'T' being the index date of sarecycline treatment initiation, the baseline data collection may transpire anytime between T= -2 weeks post-index date and T= +4 days post-index date; the 4-week follow-up data collection will happen at T=4 weeks post-index date  $\pm$  4 days; the 8-week follow-up data collection will happen at T=8 weeks post-index date  $\pm$  4 days, and 12-week follow-up data collection will happen at T=12 weeks post-index date  $\pm$  4 days. Index date is the date of initiation of sarecycline treatment, when the subject took the first sarecycline dose.

Different data elements will be collected from Site Investigators and from study Subjects at these data collection encounters, as outlined below. For patients of age 12yrs and older, acne patients themselves will complete relevant PRO elements pertinent to study endpoints, at all encounters; for patients of age 9-11yrs, parents/caregivers of pediatric patients will complete the PRO elements at all encounters, serving as a proxy, upon consulting with their child on question responses.

The schedule of events is summarized in Appendix A.

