### ***8.3.1 Investigator Assessments***

An IGA scale of 0 (Clear) to 4 (Severe) will be used by the Site Investigators to assess the severity of a subject's facial acne at the time of study encounters. The IGA should be representative of the investigator's overall general assessment of the subject's Acne and take into account the quality, as well as the quantity, of lesions. These assessments will be done at baseline encounter to document AV severity before initiation of sarecycline treatment; the assessments will be repeated by the Site Investigators at study subject follow-up encounters at Weeks 4, 8 & 12, post-index date. The comparison of follow-up assessments to the baseline assessment will help determine treatment effectiveness. It is expected that the Investigator assessments will be conducted via in-person visits/encounters at baseline and week-12, and when in-person assessments are not feasible (owing to COVID-related travel restrictions), the assessments maybe done via virtual/remote visits. The same evaluator shall perform all evaluations for a subject during the study, as feasible.

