## 17.2 Appendix B: Select Study Questionnaires

### ASIS

Please read and answer each of the following questions about **acne signs and symptoms**. Before answering each question, **look in the mirror and think about the acne on your face**. Select one answer for each question that best describes your experience with acne **right now**. There are no right or wrong answers.

1. How oily is your face right now?

Not at all	A little	Somewhat	Quite a bit	Very
				

2. How many pimples do you have on your face right now?

None	A few	Some	Quite a bit	A lot
				

3. How many acne scars (holes or indents) do you have on your face right now?

None	A few	Some	Quite a bit	A lot
				

4. How many scabs from acne do you have on your face right now?

None	A few	Some	Quite a bit	A lot
				

5. How many dark marks from acne do you have on your face right now?

None	A few	Some	Quite a bit	A lot
				

6. How many blackheads do you have on your face right now?

None	A few	Some	Quite a bit	A lot
				

7. How many whiteheads do you have on your face right now?

None	A few	Some	Quite a bit	A lot
				

8. How much redness do you have on your face right now?

None	A few	Some	Quite a bit	A lot
				

9. Overall, how is the acne on your face right now?

Clear	Almost clear	Mild	Moderate	Severe
				

Please read and answer each of the following questions about how **acne impact your quality of life**. Before answering each question, look in the mirror and think about the acne on your face. Select one answer for each question that best describes your experience with acne in the past 7 days. There are no right or wrong answers.

10. Over the past 7 days, rate how your face looked because of your acne.

Excellent	Very good	Good	Fair	Bad
				

11. Over the past 7 days, how often did you feel sad because of the acne on your face?

Never	Rarely	Some of the time	Most of the time	All of the time
				

12. Over the past 7 days, how often did you feel embarrassed because of the acne on your face?

Never	Rarely	Some of the time	Most of the time	All of the time
				

13. Over the past 7 days, how often did you feel self-conscious because of the acne on your face?

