#### 4 STUDY SCHEDULE & PROCEDURES

Study eligible patients who were considered as candidates for sarecycline treatment as part of usual care Acne management were screened, consented and recruited into the study, followed for up to 12 weeks post-index date, encompassing four distinct data collection encounters, namely, baseline, week-4, week-8 and week-12, post-index date. Index date is the date of initiation of sarecycline treatment (at baseline), when the subject was prescribed sarecycline.

Different data elements were collected from Site Investigators and from study Subjects at these data collection encounters, as outlined below. For patients of age 12yrs and older, acne patients themselves completed relevant PRO elements pertinent to study endpoints, at all encounters; for patients of age 9-11yrs, parents/caregivers of pediatric patients completed the PRO elements at all encounters, serving as a proxy, upon consulting with their child on question responses.

The schedule of events is summarized in Appendix A.

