#### **5.3.1 *Investigator Assessments***

An IGA scale of 0 (Clear) to 4 (Severe) was used by the Site Investigators to assess the severity of a subject's facial acne at the time of study encounters. The IGA is representative of the investigator's overall general assessment of the subject's Acne and takes into account the quality, as well as the quantity, of lesions. These assessments were done at baseline encounter to document AV severity before initiation of sarecycline treatment; the assessments were repeated by the Site Investigators at study subject follow-up encounters at Weeks 4, 8 & 12, post-index

date. The comparison of follow-up assessments to the baseline assessment will help determine treatment effectiveness. All Investigator assessments were conducted via in-person visits/encounters at baseline and week-12. The same evaluator performed all evaluations for a subject during the study.

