## 6.3 General Statistical Procedures

### 6.3.1 Overview

Data from Site Investigators and study Subjects will be treated separately, and combined into one dataset, based on the study assessments of interest. Validated instruments will be scored according to developer guidelines, reporting domain scores and overall summary scores, as appropriate. Home-grown questions/items will be analyzed and reported individually, based on the respective response scales. Change from Baseline (CFB) in scores (for continuous variables) or proportions (for discrete variables) will be computed as Week-12 minus Baseline measure for respective question responses.

Discrete measures will be assessed using summary statistics encompassing percentage of Subjects reporting particular outcome measures. The statistical differences in discrete variables to compare different patient groups (for subgroup analysis) for a given measure at a particular timepoint (such as Baseline or Week-12), or CFB in proportion of patients reporting a particular response to an outcome measure at a particular timepoint (such as Week-12) will be assessed using a  $\chi^2$  test. In case of likert scales, to compute P-values for CFB in proportions, the top-two response categories (of a likert scale) for a given question at Baseline will be grouped together into a single group proportion (versus the rest of the population/responders all together) and compared to the same group proportion at Week-12; the procedure will be repeated for the bottom-two response categories (of a likert scale) for a given question, by grouping them together into a single group proportion and compare it to the same group proportion at Week-12. For example, for ASIS item # 1 (how oily is your face right now), proportion of patients reporting “Not at all/A little” at Baseline will be grouped together (vs. rest of the population/responders) and compared to proportion of patients reporting “Not at all/A little” at Week-12; similarly, proportion of patients reporting “Quite a bit/Very” at Baseline will be grouped together and compared to proportion of

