## 12.1 Appendix A: Study Schedule of Events

Study Encounter (physical or virtual)	Baseline E1	E2	E3	End of Study E4	Early Termination Visit
Week †		Wk 4 (± 4 d)	Wk 8 (± 4 d)	Wk 12 (± 4 d)	-
Informed consent	X				
Selection criteria	X				
Demographics & baseline clinical characteristics 	X				
Physical examination 	X			X	X
AV medical history and relevant comorbidites 	X			X	X
Seysara dose 	X	X	X	X	X
Dispensing and return of study medication	X	X	X	X	X
Prior acne medication (since diagnosis & past 6 months)	X				
Concomitant general medication	X			X	X
Concomitant anti acne medication	X			X	X
Site Investigator's clinical assessment of acne 	X	X	X	X	X
Study subject questionnaires 	X	X	X	X	X
AEs/SAEs 	X	X	X	X	X
Reasons for premature study withdrawal					X

† Expected in-person or virtual encounter/visit schedule, in relation to the index date (date of first administration of sarecycline).

 Clinical characteristics data assessed retrospectively based on what is documented in patient medical charts.

 Routine physical examination conducted as part of usual care alone and as documented in patient medical charts; such data may include - blood pressure, waist circumference, height/weight measurements.

 May include AV date of diagnosis, baseline severity, relevant comorbidities, per clinician judgment and/or as documented in patient medical charts immediately before the index date; new emerging comorbidities during the study period will be recorded, based on the documentation in patient medical charts.

 Expected usage is once daily, every day during the duration of the trial.

 Site Investigator assessments of AV severity of Subjects may be conducted during subject visit to clinician offices, or via remote/virtual (telehealth) visits owing to Covid-related travel restrictions.

 Subject self-assessments will include PtGA of acne severity; various HRQOL assessments will be conducted at baseline and Week 12.

 In the case of premature study discontinuation due to an AE, the Investigator should make every effort to collect the AE duration and outcome. Any SAE that is ongoing at the End of the Study or at the time of premature withdrawal will be followed up until the SAE is resolved or at least up to 4 weeks. AE follow-up information will be reported in the eDCF.

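### The protocol permits baseline data up to 4 days after the first dose and the SAP sets no pre-dose condition, so some PRO changes from baseline may be modestly biased

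*Protocol*

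**What the plan says.** **Window.** Protocol section 7: "the baseline data collection may transpire anytime between T= -2 weeks post-index date and T= +4 days post-index date". The same section fixes T: "Index date is the date of initiation of sarecycline treatment, when the subject took the first sarecycline dose". Days +1 to +4 are therefore on treatment by the protocol's own definition. Protocol 7.2 has the subject record that first-dose date in the app.

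**Intended timing.** For the IGA, Protocol 8.3.1 says "These assessments will be done at baseline encounter to document AV severity before initiation of sarecycline treatment", and SAP 5.3.1 reports it as done: "These assessments were done at baseline encounter to document AV severity before initiation of sarecycline treatment". For the subject's own severity ratings, Protocol 8.3.2 and SAP 5.3.2 are looser. They tie baseline to the time at which sarecycline is started and do not require it to come first.

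**Calculation.** SAP 6.3.1 says that change from baseline "will be computed as Week-12 minus Baseline measure for respective question responses". No condition is placed on when the baseline record was made. The sensitivity analyses in SAP 6.11 cover LOCF and remote visits only.

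**Index date in the SAP.** SAP section 4 does not restate the window and says "Index date is the date of initiation of sarecycline treatment (at baseline), when the subject was prescribed sarecycline". SAP Appendix A sets visits "in relation to the index date (date of first administration of sarecycline".

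**Recall.** ASIS items 1-9 ask about the present moment. Items 10-17, the whole Impact domain, look back over a week, for example "Over the past 7 days, rate how your face looked because of your acne". Items 1, 4 and 10 of the Expert Panel Questionnaire (EPQ), as numbered in Appendix B, also name a 7-day period.

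**The concern.** A change from baseline in a single-arm study needs a reference taken before treatment, because no control group offsets a contaminated one. A baseline completed on days +1 to +4 can already contain early drug effect and the expectation that comes with having started treatment. Improvement before the baseline record shrinks the measured change; early worsening inflates it.

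The PRO surveys are the more exposed part. Subjects complete them by weblink or app, at enrollment or within a few days of recruitment (Protocol 7.1). Their baselines feed the paired t-tests and the change-in-proportion p-values in the SAP. Someone programming from SAP section 4 alone would not see the issue, because that section has no window and ties the index date to the prescription.

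What is at stake is the ASIS and EPQ change-from-baseline results, which are additional endpoints.

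**Working it through.** The plan gives no figure to reproduce: there is no power calculation, and neither the response time course nor the share of post-dose baselines is stated.

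**1. Visit windows.** Week 12 is day 84 ± 4 and baseline is day -14 to +4. The baseline-to-Week-12 gap therefore runs from 84 - 4 - 4 = 76 to 84 + 4 + 14 = 102 days. With baseline no later than the first dose it runs from 84 - 4 = 80 to 102 days. Only the lower end moves.

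**2. Loss for one subject with a day +4 baseline.** Let F(t) be the improvement by day t, assumed to be either linear (t/84) or exponential, 1 - exp(-kt) with k = ln 2 / half-time.

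- *Present-moment items:* loss = F(4)/F(84).
- *7-day-recall items:* loss = mean of F over days -3 to +4 (zero before the dose) divided by mean of F over days 77 to 84. Four of the seven recalled days (57%) are on treatment, but the three untreated days and the small early effects pull the average down.

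| Assumed curve | Present-moment items | 7-day-recall items |
|---|---|---|
| Linear | 4/84 = 4.8% | 0.0136/0.9583 = 1.4% |
| Exponential, 28-day half-time | 0.0943/0.8750 = 10.8% | 0.0274/0.8635 = 3.2% |
| Exponential, 14-day half-time | 0.1797/0.9844 = 18.3% | 0.0530/0.9813 = 5.4% |

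**3. Cohort mean.** Attenuation = f × loss, where f is the share of subjects with a day +4 baseline. Taking f = 10% and 25% (assumed):

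| Assumed curve | Present-moment, 10% / 25% | 7-day recall, 10% / 25% |
|---|---|---|
| Linear | 0.5% / 1.2% | 0.1% / 0.4% |
| 28-day half-time | 1.1% / 2.7% | 0.3% / 0.8% |
| 14-day half-time | 1.8% / 4.6% | 0.5% / 1.4% |

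Baselines on days +1 to +3 would lose less. As a fast extreme, a 7-day half-time gives 32.7% per subject for present-moment items, and 3.3% / 8.2% for the cohort.

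**4. IGA success.** Entry requires IGA 3 or 4. SAP 6.5 requires a drop of at least 2 points and a Week 12 score of 0 or 1.

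| Recorded baseline | Week 12 = 0 | Week 12 = 1 | Week 12 = 2 or more |
|---|---|---|---|
| 4 | success | success | no |
| 3 | success | success | no |
| 2 (not eligible) | success | no | no |

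Baselines 3 and 4 give the same result. Eligibility also fixes the baseline IGA proportions at 0% clear or almost clear and 100% moderate or severe, so the IGA change-in-proportion tables do not move either. Only a recorded baseline below 3 would change anything.

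**The case against.** The strongest reply is that a post-dose baseline is allowed but probably uncommon. Baseline is expected at or soon after enrollment, and drug is shipped to the site only after the decision to prescribe (Protocol 7.2). The investigator's baseline data rest on the chart or on the encounter at which sarecycline was prescribed (Protocol 7.1). The baseline IGA in SAP Table 7.2.4.1 is item S9A, whose label suggests that it was collected with the selection items; that is an inference. The primary endpoint is descriptive PRO levels at Week 12, and the SAP treats its p-values as exploratory. All of this stands and limits the stakes. It does not remove the contradiction over the IGA or supply the missing rule for the PROs.

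Three stronger readings are tempting, and the documents do not support them:

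- *That some baselines were in fact on treatment.* The protocol permits this; no document reports a case or a count.
- *That every change from baseline is distorted.* Only subjects with a post-dose record are affected, and the direction depends on whether they first improved or worsened.
- *That IGA success is biased.* Step 4 shows no effect for recorded baselines of 3 or 4. A subject rated 2 at baseline would fail the entry criterion. Protocol 3.2 and the SAP table notes speak of a 2-point decrease. Read as exactly 2, that would make success depend on 3 versus 4, but SAP 6.5 says at least 2.

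Nor do the documents say that baseline PROs must come before the first dose; that requirement is explicit only for the IGA.

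**Conclusion.** The point holds in a limited form. Protocol section 7 contradicts the pre-treatment timing stated for the IGA, the SAP has no pre-dose condition for any baseline, and its two index-date definitions disagree. Some baseline PROs may therefore be on-treatment values, which would bias the ASIS and EPQ changes for those subjects.

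The size is modest. For a day +4 baseline, the loss is about 5-18% of a subject's change on present-moment items and about 1-5% on 7-day-recall items. The effect on the cohort mean is probably a few percent or less. These figures assume steady improvement from the first dose along the curves shown, with 10-25% of subjects affected. The effect becomes large only if most baselines are post-dose and response is fast. The weakness does not invalidate the study.

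**What to change.** 1. Reconcile the baseline window in Protocol section 7, and the index-date definitions in Protocol section 7, SAP section 4 and SAP Appendix A, with the stated pre-treatment intent.
2. In the SAP, define baseline for ASIS, EPQ and IGA as the last record dated on or before the app-recorded first dose. Where only a later record exists, flag it.
3. Report how many baselines fall on days +1 to +4, separately for PROs and IGA. A zero count for the IGA would confirm the statement in SAP 5.3.1; otherwise that statement needs correcting.
4. Repeat the PRO change tables (7.1.6.2, 7.1.9, 7.1.10, 7.1.13 and 7.1.15) without the flagged subjects. IGA tables need repeating only if a post-dose baseline IGA below 3 is recorded.

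The SAP already describes enrollment and follow-up in the past tense, so its rule is the practical remedy. The cost is a few lines of text and one date comparison. The SAP already uses the first-dose date to classify concomitant medications (6.7) and to bound adverse events (the Table 7.4.4 series). The downside is that a few subjects drop out of the repeat analysis.

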### 7.1 Enrollment/Baseline (Encounter # 1)

Baseline data collection will take place at the time of subject enrollment into the study or within a few days of recruitment. The subject encounters are expected to take place during in-person subject visits to the clinic, but remote/virtual visits will be allowed where Covid-related protocols prevent in-person visits. The recruited Site Investigators and study Subjects will be sent a weblink to the eDCFs and survey respectively for their completion. Subjects will be able to access the surveys on their mobile phone, using a study-specific Mobile App.

The following data elements will be collected at baseline, from patient medical charts and/or per Site Investigator's best clinical judgement based on their recent encounter with the study subject

---

while prescribing sarecycline as part of usual care and based on subject's recent past medical history:

- Demographics (e.g., age, gender).
- General clinical characteristics, as documented in medical charts (incl. blood pressure, waist circumference, height/weight measurements, comorbidities).
- AV disease characteristics (AV history; current IGA of AV severity in face).
- Past AV treatment history (used ever, and those used within the past 6 months).
- Sarecycline treatment characteristics (dose, frequency, date of recommendation).
- Concomitant medications (for AV and comorbidities).
- Perceptions about antibiotics/antibiotic resistance.

The following data elements will be collected at baseline, from study Subjects, via online survey portal or a mobile app:

- Demographics (e.g., gender, race/ethnicity, education, employment/school status, living status).
- Perceptions of AV-related symptoms and impact of AV on emotional functioning, social functioning and activities of daily living.
- Perceptions about antibiotics/antibiotic resistance (asked in only Adult Subjects).

In case of pediatric patients, Caregivers will also complete a battery of questions related to their own perceptions of antibiotics/antibiotic resistance, their child's current acne severity, and impact of acne on their child.

In a small subset of sites, Site Investigators may utilize Canfield® photography equipment to take photographs of patient's face to document the baseline AV severity of acne patients in the study, during in-person patient visits.

## 7.2 Shipment of Study medication

Following the Site Investigator's decision to prescribe sarecycline (Seysara®) to study eligible patients, a commercial supply of the appropriate dose and quantity of study medication will be shipped to the attention of Site Investigator at their clinic/site. The study Subjects will be asked to record the first day of administration of sarecycline via the mobile app, and this date will constitute the study 'index date', upon which the follow-up encounter timepoints (at weeks 4, 8 & 12) will be determined.

## 7.3 First Follow-up Encounter (Encounter # 2)

At the completion of 4 weeks ( $\pm$  4 days) post-index date, the Site Investigator and Subjects will be asked to complete the first follow-up data collection, conducted via in-person or virtual/remote visits.

The patients will be advised to visit their site/clinician's offices to do the following:

- Drop off the first tablet/pill bottle of Seysara® (bottle # 1) supplied to them at study start, be it empty or with left-over pills.
  - This may be done as curb-side interaction, without entering clinician's offices.
- Pick-up the second bottle of Seysara® supply (bottle # 2) for the next four weeks of use.
  - This may be done as curb-side interaction, without entering clinician's offices.
- Undergo AV clinical evaluation inside clinician's office, if feasible.

The Site Investigators will complete the following, based on the information documented in patient medical charts and per clinical judgment guided by observing study subject via in-person or virtual/remote visit:

- IGA of current AV severity on the face.
- Patient treatment compliance, per sarecycline pill/tablets left over in the subject-returned bottle.

- Modifications to sarecycline treatment characteristics (e.g., change in dose, discontinuation), in the past 4 weeks, if any.
- AEs (incl. SAEs) related to or possibly related to sarecycline, observed in the past 4 weeks, as documented in the medical charts.
- Information on withdrawal from study (if occurred within the past 4 weeks).

The study Subjects will provide the following information via online survey portal or a mobile app: perceptions of current AV-related signs/severity. In case of pediatric patients, this information will be obtained from parents/caregivers as well.

